4.2. Discussion of Study Design, Including the Choice of Control Groups

This study is designed as a multi-center, single-arm, open-label clinical study to clinically validate a *gyrA* assay used to determine ciprofloxacin susceptibility in the treatment of uncomplicated gonococcal infection by assessing the efficacy of ciprofloxacin for treatment of uncomplicated *N. gonorrhoeae* infections with serine 91 *gyrA* genotype as identified by the *gyrA* assay.

As the study is designed to assess the ability of the *gyrA* assay to correctly detect subjects with ciprofloxacin-susceptible *N. gonorrhoeae* infections, only subjects with infections positively identified by the assay are enrolled and all subjects are treated with ciprofloxacin (i.e. there is no control group for this study).

4.3. Selection of Study Population

Subjects must meet all of the inclusion criteria in order to be eligible to participate in the study. Subjects who present with a new *N. gonorrhoeae* infection may be rescreened for eligibility. No exemptions are granted on Subject Inclusion/Exclusion Criteria in DMID-sponsored studies.

1. Willing and able to give voluntary written informed consent before any study related procedure is performed.
2. 18 years or older on the day of enrollment.
3. Untreated *gyrA* serine 91 genotype *N. gonorrhoeae* of the rectum, or male or female urogenital tract*, as determined by the *gyrA* test assay on a specimen collected within 30 days of enrollment.
*Subjects must have *gyrA* serine 91 genotype detected for *N. gonorrhoeae* from at least one non-pharyngeal site.
4. Willing to abstain from sexual intercourse or use condoms during any sexual contact until the Test of Cure Visit (Visit 2, Day 5-10) is complete.
5. Women of childbearing potential* must have no vaginal intercourse 14 days before enrollment or use an effective birth control method ** for 30 days before enrollment and agree to continue through visit 2.
*A woman is considered of childbearing potential unless post-menopausal (>2 years) or surgically sterilized (tubal ligation >1 year, bilateral oophorectomy, or hysterectomy).
**Acceptable birth control methods for the purposes of this study may include abstinence from intercourse with a male partner, monogamous relationship with vasectomized partner, male condoms with the use of applied spermicide, intrauterine devices, and licensed hormonal methods. A highly effective method of contraception is defined as one that results in a low failure rate (i.e., less than 1% per year) when used consistently and correctly.
6. Able to swallow pills.
7. Willing to comply with protocol requirements, including availability for follow-up for the duration of the study.
8. Agree to avoid systemic or intravaginal antibiotics* with activity against *N. gonorrhoeae* from enrollment through Visit 2 (Day 5-10).
*Topical and intravaginal antifungals are permitted.
9. Agree to avoid magnesium/aluminum antacids, sucralfate, didanosine, or highly buffered drugs, up to 2 hours after receipt of study drug.

Subjects meeting any of the following criteria at enrollment will be excluded from the study:

1. Known renal insufficiency from clinical history.
2. Use of systemic or intravaginal antibiotics* with potential activity against *N. gonorrhoeae* within 30 days prior to study drug administration.
*Topical and intravaginal antifungals are permitted.
3. Use of systemic corticosteroid drugs or other immunosuppressive therapy within 30 days prior to enrollment.

4. Receipt or planned receipt of an investigational product in a clinical trial within 30 days prior to or 7 days after treatment administration.
5. Pregnant or breastfeeding.
6. Clinical diagnosis of pelvic inflammatory disease or genital ulcer.
7. Confirmed or suspected complicated or systemic gonococcal infection, such as abdominal pain, testicular pain, epididymitis, orchitis, arthritis, or endocarditis.
8. Receipt of magnesium/aluminum antacids, sucralfate, didanosine, or highly buffered drugs, within 6 hours before receipt of study drug.
9. Mutant *N. gonorrhoeae* *gyrA* serine 91 genotype from any anatomic site, as determined by the *gyrA* test assay on a specimen collected within 30 days of enrollment.
10. Known allergy or history of adverse reaction to ciprofloxacin.
11. Known allergy to quinolones.
12. Previous enrollment in this study.
13. Medical condition or other factor that in the judgment of the investigator might affect ability to comply with procedures.

Subjects may withdraw or be withdrawn from the study for any of the reasons given below. The reason for withdrawal is recorded in the data collection form.

- Subject vomits within 1 hour of study medication administration.
- Subject receives any systemic antibiotic other than the study medication prior to Visit 2 (Day 5-10).
- Subject is pregnant or breastfeeding.
- Discretionary decision by the site investigator.
- At the discretion of the Institutional Review Board (IRB), National Institutes of Health (NIH), or other government agency as part of their duties to ensure that research subjects are protected.

Subjects who withdraw voluntarily prior to receiving ciprofloxacin are offered local standard of care treatment for *N. gonorrhoeae* and followed per clinic guidelines.

Subjects who withdraw voluntarily or never return after receiving ciprofloxacin and tolerated medication without difficulty are not contacted for repeat gonorrhea testing or treatment.

Subjects who withdraw voluntarily or never return after being found to be positive for *N. gonorrhoeae* at Visit 2 (Day 5-10) are contacted by phone and by certified mail with instructions that they should follow-up for treatment per local standard of care and should be followed per clinic guidelines.

Although the study sponsor has every intention of completing the study, the sponsor reserves the right to terminate the study at any time for clinical or administrative reasons.

4.4. Treatments

4.4.1. Treatments Administered

Subjects with *gyrA* serine 91 genotype rectal or urogenital *N. gonorrhoeae* receive one directly observed dose of ciprofloxacin 500 mg. Subjects are observed in the clinic for at least 5 minutes after receiving ciprofloxacin and are instructed to return to the clinic or to contact the study site coordinator immediately if they vomit within 1 hour of receiving ciprofloxacin. Subjects who vomit within 1 hour of study drug administration should be retreated for *N. gonorrhoeae* infection with an alternative recommended regimen per local standard of care.

The dates of the treatment are presented for subjects in the Safety population by site in [Table 3](#).

4.4.2. Identity of Study Product(s)

Ciprofloxacin is a quinolone medication approved by the FDA for the treatment of gonorrhea. Ciprofloxacin hydrochloride, USP, a fluoroquinolone, is the monohydrochloride monohydrate salt of 1- cyclopropyl-6-fluoro-1, 4-dihydro-4-oxo-7-(1piperazinyl)-3-quinolinecarboxylic acid. The molecular weight of the ciprofloxacin hydrochloride monohydrate is 385.82. It is a faintly yellowish to light yellow crystalline substance.

Ciprofloxacin will be supplied as 500 mg tablets.

4.4.3. Method of Assigning Subjects to Treatment Groups (Randomization)

Not applicable.

4.4.4. Selection and Timing of Dose for Each Subject

Subjects with *gyrA* serine 91 genotype rectal or urogenital *N. gonorrhoeae* receive one dose of ciprofloxacin 500 mg by mouth under direct observation with the date and time of administration documented.

4.4.5. Blinding

Not applicable. This is an unblinded study.

4.4.6. Prior and Concomitant Therapy

Medications history (concomitant medications contraindicated with ciprofloxacin) include a review of all current medications and medications taken 30 days prior to study enrollment. Assessment of eligibility also include a review of all permitted and prohibited medications per the Subject Inclusion and Exclusion Criteria (see Section [4.3](#)).

Administration of any contraindicated medications or new antibiotics after enrollment are recorded on the appropriate data collection form.

Contraindicated medications include all medications contraindicated with ciprofloxacin (described in Section [4.3](#)) taken 30 days prior to signing the informed consent form through Visit 2 or early termination, whichever occurs first.

Subjects who have received study medication and are subsequently diagnosed with a concomitant infection, which requires systemic antibiotics receive treatment according to the local clinic's standard of care.

Use of new medication should prompt evaluation for the presence of a new diagnosis of chronic medical disease or condition.

Oral contraceptives are allowed, as they do not alter the metabolism of ciprofloxacin.

4.4.7. Treatment Compliance

All subjects with *gyrA* serine 91 genotype rectal or urogenital *N. gonorrhoeae* will receive single dose of directly observed ciprofloxacin 500 mg in the clinic.

Subjects are observed for at least 5 minutes after administration of ciprofloxacin and are instructed to return to the clinic or to contact the study site coordinator immediately if they vomit within 1 hour of receiving study medication. Subjects who vomit within 1 hour of study drug administration are retreated for *N. gonorrhoeae* infection with an alternative recommended regimen per the local standard of care.

See Section 3.3.6 for the definition of treatment compliance.

4.5. Efficacy and Safety Variables

General principles for safety and efficacy analyses are to accept multiple observations within a specific visit period. In the case of multiple observations within a specific window, the assessment value that is closest to the scheduled visit window will be used in the analyses for the post-baseline records. The last observed values prior to administration of ciprofloxacin will be used as the baseline value. All the recorded data will be listed. If observations have the same distance to the scheduled assessment, the latest one will be used.

4.5.1. Safety Variables

Ciprofloxacin has a well-established safety profile and has been prescribed to several millions of people in the United States (US) and worldwide as it was the CDC's recommended treatment regimen for uncomplicated gonorrhea from 1993 to 2007. Therefore, adverse event assessment is not required for this study.

In order to address the FDA Drug Safety Communication dated May 12, 2016, regarding fluoroquinolone use for certain uncomplicated infections, subjects are asked at Visit 1, Visit 2, and any Unscheduled or Early Termination Visit if they have experienced any serious side effects related to fluoroquinolone use. These include tendon pain, joint pain, muscle pain, tingling or pricking sensation, confusion, and hallucinations. This information is recorded in the study source documents as a change in health status.

Any subject who experiences such an event is given instructions on how to submit a MedWatch Consumer Voluntary Reporting Form to the FDA if they desire.

Side effects of fluoroquinolone use will be summarized for all enrolled subjects (see Section 9).

4.5.2. Efficacy Variables

See Section 3.3 for efficacy variable definitions.

5. SAMPLE SIZE CONSIDERATIONS

The primary analysis will compute the proportion of ciprofloxacin-susceptible *N. gonorrhoeae*-infected subjects with microbiological cure 5-10 days after receiving ciprofloxacin in the per-protocol analysis population. The confidence interval for the microbiological cure proportion will be computed using a one-sided modified Jeffreys interval using a significance level of 0.05. Power calculations were performed via a simulation study based on 10,000 replications assuming a 98% microbiological cure rate.

Figure 1 presents the power available to test that the microbiological cure rate is at least 95% (i.e., lower bound of the one-sided confidence interval is at least 95%) across a range of evaluable sample sizes. Here, evaluable denotes eligible for the PP analysis population. The power reaches 80% at a sample size of 195 evaluable subjects; however, since the power curve is not monotonic, sample sizes directly on either side of 195 are below 80%. Since the exact number of evaluable subjects at the end of the study is difficult to predict, an evaluable target of 257 subjects is chosen to ensure at least 80% even if the exact number of evaluable subjects at the end of the study differs slightly from 257. With a target of 257, the power available is approximately 85% and we can fall at most 10 subjects short (sample size of 247 evaluable subjects) and still ensure 80% power. Any sample size greater than 257 will ensure at least 80% power.

To calculate the number of subjects required to enroll to reach 257 subjects in the PP analysis population, the following assumptions are made:

- 25% of enrolled subjects will be culture negative at baseline.
- 10% of subjects will be excluded from the PP analysis population (reasons for exclusion are stated in Section 6.3)

Under these assumptions, enrolling 381 subjects will provide 257 subjects in the PP analysis population. Since the proportion of subjects who will be culture negative at baseline can vary depending on a number of factors, 25% is a rough estimate. The exact number of subjects needed to provide 257 subjects in the PP analysis population may vary from 381, so 381 is an approximate enrollment target.

6. GENERAL STATISTICAL CONSIDERATIONS

6.1. General Principles

Tabulations will be used extensively to summarize the data. All continuous variables will be summarized using some or all of the following descriptive statistics: n (samples size), mean, standard deviation, median, maximum, and minimum. The frequency and percentages (based on the sample size) of observed levels will be reported for all categorical measures. Modified Jeffreys confidence intervals (CIs) for binomial proportions will be computed for efficacy variables [2]. A 5% one-sided significance level will be used; i.e. one-sided 95% confidence intervals will be generated. In general, all data will be listed, sorted by site and subject, and when appropriate by visit number within subject. All summary tables will be annotated with the total population size relevant to that table, including any missing observations.

Note that in the data listing, Subject ID is the unique subject identifier, not the Study ID used on study, and dates will not be included, only Study Day. Study Day 1 will be the day of the dose of treatment.

6.1.1. Pseudo Code

The following SAS® pseudo code will be used to calculate the following:

Lower bound of the one-sided 95% Jeffreys CI for proportions/percentages if the number of cures is less than the number of subjects included in the analysis:

```
proc freq;  
    tables cure / alpha=0.1 binomial(jeffreys);  
run;
```

Lower bound of the one-sided 95% Jeffreys CI for proportions/percentages if the number of cures is equal to the number of subjects (n) included in the analysis:

```
CI_Lower = 0.05** (1/n);
```

95% Wilson CI for proportions/percentages:

```
proc freq;  
    Table treatment*analysisvariable / alpha=0.1 binomial(wilson);  
    ods output binomialcls=outputdsn;  
run;
```

95% Exact Blaker CI for proportions/percentages:

```
proc freq;  
    Table treatment*analysisvariable / alpha=0.1 binomial(blaker);  
    ods output binomialcls=outputdsn;  
run;
```

95% Agresti-Coull CI for proportions/percentages:

```
proc freq;  
    Table treatment*analysisvariable / alpha=0.1 binomial(AC);  
    ods output binomialcls=outputdsn;  
run;
```

6.2. Timing of Analyses

The final analysis will be performed after database lock when all subjects have been followed through Visit 3, the final study visit.

6.3. Analysis Populations

6.3.1. Safety Analyses

There are no formal analyses of safety data (see Section 4.5.1 and Section 9).

6.3.2. Efficacy Analyses

All efficacy analyses will be performed in the Per Protocol (PP), microbiological Intent-to Treat (micro-ITT) and Intent-to-Treat (ITT) analyses populations.

6.3.2.1. Intent-to-Treat Analysis (ITT) Population

The ITT analysis population includes all enrolled subjects, regardless of whether they received study treatment or were compliant with the administration procedures or schedule.

Subjects with non-evaluable outcome status will be included in the ITT analysis population and classified as microbiological failures. Subjects who receive any treatment other than the study medication for their *N. gonorrhoeae* infection will be included in all efficacy analyses as treatment failures. Subjects who discontinued early from the study with lack of treatment effect being the documented reason for discontinuation will be included as microbiological failures. Subjects who vomited within 1 hour of administration will be included as microbiological failures.

6.3.2.2. Microbiological Intent-to-Treat (micro-ITT) Population

For the primary analysis, the micro-ITT population includes all enrolled subjects who have wild type *gyrA* serine 91 *N. gonorrhoeae* isolated from the rectum or urogenital site on Day 1 culture. Subjects with infections at multiple anatomic sites are included as long as one of the infected sites is the rectum or urogenital site. Subjects with infections at multiple anatomic sites must be wild-type at each culture-positive site to be included in the primary analysis.

Subjects with non-evaluable outcome status will be included in the micro-ITT population and classified as microbiological failures. Subjects who discontinued early from the study with lack of treatment effect being the documented reason for discontinuation will be included as microbiological failures. Subjects who vomited within 1 hour of administration will be included as microbiological failures.

For the analysis of secondary objective 1, subjects need to have wild type *gyrA* serine 91 *N. gonorrhoeae* isolated on Day 1 culture at the particular anatomical site being assessed. The results at the other anatomical sites will not be considered when determining a subject's eligibility into each of the site-specific populations.

There will be four micro-ITT populations identified:

- Primary micro-ITT population
- Rectal micro-ITT population
- Urogenital micro-ITT population
- Pharyngeal micro-ITT population

6.3.2.3. Per Protocol Population

For the primary outcome measure, the PP population includes enrolled subjects who met all inclusion/exclusion criteria, have wild type *gyrA* serine 91 *N. gonorrhoeae* isolated on Day 1 culture from the rectum or urogenital site, have an evaluable microbiological outcome status (see Section 3.3.2), complied with study treatment, did not receive any contraindicated medication or systemic antibiotic other than the study medication for any infection prior to Visit 2, and returned for their Visit 2 (Test of Cure) visit within window. Subjects with infections at multiple anatomic sites are included as long as one of the infected sites is the rectum or urogenital site.

In addition, subject who are infected at multiple anatomic sites must meet either of the two following criteria to be included in the PP population:

- wild-type at each culture positive site, or
- wild-type at the rectum/urogenital site and unknown *gyrA* status at the pharyngeal site (due to indeterminate or missing result).

For subjects who meet the second criteria above, the pharyngeal results will be ignored in the determination of cure status.

For the PP analysis population, subjects with non-evaluable outcome status will be excluded from the analysis. Subjects who discontinued early from the study with lack of treatment effect being the documented reason for discontinuation will be included as microbiological failures.

For the analysis of secondary objective 1, subjects need to have wild type *gyrA* serine 91 *N. gonorrhoeae* isolated on Day 1 culture at the particular anatomical site being assessed. In addition, alternate per-protocol analyses which exclude subjects with reported concomitant infection/disease/procedure that may interfere with study product, use of concomitant medications or products that may interfere with study product, significant protocol deviations, and other events that may impact study product effectiveness or study analyses will be explored. Exclusions from this alternate PP population will be determined on a case-by-case basis prior to database lock.

There will be four PP populations and identified based on wild type *gyrA* serine 91 *N. gonorrhoeae* isolation at Day 1 for a particular site. The results at the other anatomical sites will not be considered when determining a subject's eligibility into each of the site-specific populations.

- Primary PP population
- Rectal PP population
- Urogenital PP population
- Pharyngeal PP population

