15. Once swabs have been collected, and all eligibility criteria have been assessed, subjects will receive one dose of ciprofloxacin 500 mg by mouth under direct observation with the date and time of administration documented.
 - Subjects will be observed for at least 5 minutes after administration of ciprofloxacin.
 - Subjects will be instructed to return to the clinic or to contact the study site coordinator immediately if they vomit within 1 hour of receiving study medication.
 - Subjects who vomit within 1 hour of study drug administration will be retreated for *N. gonorrhoeae* infection with an alternative recommended regimen per the local standard of care.
 16. Reminder to abstain from sexual intercourse or use condoms during any sexual contact until the Test of Cure Visit (Visit 2, Day 5-10) is complete
 17. Reminder to bring sex partners in for testing and treatment, if needed
 18. Reminder to return for Visit 2 (Day 5-10)

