11 STATISTICAL CONSIDERATIONS

11.1 Study Hypotheses

The primary objective of the study is to clinically validate a *gyrA* assay used to determine ciprofloxacin susceptibility in the treatment of uncomplicated gonococcal infection by assessing the efficacy of ciprofloxacin for treatment of uncomplicated *N. gonorrhoeae* infections with serine 91 *gyrA* genotype as identified by the *gyrA* assay.

The study is designed to test the following hypothesis in the primary efficacy analysis conducted in the per-protocol (PP) analysis population:

Null hypothesis: The proportion of ciprofloxacin-susceptible (as identified by the *gyrA* assay) *N. gonorrhoeae*-infected subjects with microbiological cure 5-10 days after receiving ciprofloxacin is less than 0.95.

Alternative hypothesis: The proportion of ciprofloxacin-susceptible (as identified by the *gyrA* assay) *N. gonorrhoeae*-infected subjects with microbiological cure 5-10 days after receiving ciprofloxacin is at least 0.95.

The cut-off of 0.95 was chosen based on the CDC criteria for treatments of uncomplicated *N. gonorrhoeae* infections. The criterion for recommended treatments is a cure rate of greater than 95% with a lower bound of the 95% confidence interval of at least 95%. The criterion for alternative treatments is a cure rate of greater than 95% with a lower bound of the 95% confidence interval of at least 90%.

[figure not shown]

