11.2 Sample Size Considerations

The primary analysis will compute the proportion of ciprofloxacin-susceptible *N. gonorrhoeae*-infected subjects with microbiological cure 5-10 days after receiving ciprofloxacin in the PP analysis population. The confidence interval for the microbiological cure proportion will be computed using a one-sided modified Jeffreys interval using a significance level of 0.05. Power calculations were performed via a simulation study based on 10,000 replications assuming a 98% microbiological cure rate.

Figure 11.2 below presents the power available to test that the microbiological cure rate is at least 95% (i.e., lower bound of the one-sided confidence interval is at least 95%) across a range of evaluable sample sizes. Here, evaluable denotes eligible for the PP analysis population. The power reaches 80% at a sample size of 195 evaluable subjects; however, since the power curve is not monotonic, sample sizes directly on either side of 195 are below 80%. Since the exact number of evaluable subjects at the end of the study is difficult to predict, an evaluable target of 257 subjects is chosen to ensure at least 80% even if the exact number of evaluable subjects at the end of the study differs

slightly from 257. With a target of 257, the power available is approximately 85% and we can fall at most 10 subjects short (sample size of 247 evaluable subjects) and still ensure 80% power. Any sample size greater than 257 will ensure at least 80% power.

Figure 11.2: Power Available to Test That the Microbiological Cure Rate Is at Least 95%

To calculate the number of subjects required to enroll to reach 257 subjects in the PP analysis population, the following assumptions are made:

- 25% of enrolled subjects will be culture negative at baseline.
- 10% of subjects will be excluded from the PP analysis population (reasons for exclusion are stated in section 11.4.1)

Under these assumptions, enrolling 381 subjects will provide 257 subjects in the PP analysis population. Since the proportion of subjects who will be culture negative at baseline can vary depending on a number of factors, 25% is a rough estimate. The exact number of subjects needed to provide 257 subjects in the PP analysis population may vary from 381, so 381 is an approximate enrollment target.

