11.4.1 Analysis Populations

Per-Protocol (PP) Population: This analysis population includes enrolled subjects who met all inclusion/exclusion criteria, have *N. gonorrhoeae* isolated on Day 1 culture from the rectum or urogenital site, have an evaluable microbiological outcome status (see section 11.4.3.1), complied with study treatment, did not receive any contraindicated medication or systemic antibiotic other than the study medication for any concomitant infection prior to Visit 2 (Day 5-10), and returned for their Visit 2 (Test of Cure) visit within window.

To be compliant with study treatment, a subject must be able to swallow the pill and not vomit within 1 hour of administration.

For the primary analysis, subjects need only have *N. gonorrhoeae* isolated on Day 1 culture from the rectum or urethra (male) or cervix/vagina (female). For the analysis of secondary objective 1, subjects need to have *N. gonorrhoeae* isolated on Day 1 culture at the particular site being assessed.

In addition, alternate per-protocol analyses which exclude subjects with reported concomitant infection/disease/procedure that may interfere with study product, use of concomitant medications or products that may interfere with study product, significant protocol deviations, and other events that may impact study product

effectiveness or study analyses will be explored. Details will be described in the separate statistical analysis plan.

Microbiological Intent-to-Treat (micro-ITT) Population: This analysis population includes all enrolled subjects who have *N. gonorrhoeae* isolated from the rectum or urogenital site on Day 1 culture.

For the primary analysis, subjects need only have *N. gonorrhoeae* isolated on Day 1 culture from the rectum or urethra (male) or cervix/vagina (female). For the analysis of secondary objective 1, subjects need to have *N. gonorrhoeae* isolated on Day 1 culture at the particular site being assessed.

Intent-to-Treat (ITT) Population: This analysis population includes all enrolled subjects.

Subjects who receive any treatment other than the study medication for their *N. gonorrhoeae* infection will be included in all efficacy analyses as treatment failures.

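### Protocol and SAP contradict each other, and the SAP itself, on whether a subject given other gonorrhea treatment before Visit 2 is a per-protocol failure or is excluded

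*SAP*

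**What the plan says.** **Other gonorrhea treatment before Visit 2.**

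- Protocol 11.4.1 removes from PP subjects who took a contraindicated medication, or a systemic antibiotic for a *concomitant* infection, before Visit 2. The same section says that a subject given any treatment other than the study drug for the gonorrhea "infection will be included in all efficacy analyses as treatment failures".
- SAP 6.3.2.3 restates the PP condition without the word concomitant: the subject "did not receive any contraindicated medication or systemic antibiotic other than the study medication for any infection prior to Visit 2".
- SAP 6.3.2.1 repeats the protocol's failure sentence, but inside the ITT paragraph. SAP 6.3.2 says that all efficacy analyses are run in PP, micro-ITT and ITT. Neither 6.3.2.2 (micro-ITT) nor 6.3.2.3 (PP) carries the sentence.
- SAP Table 4 still gives the PP exclusion reason as an antibiotic for a concomitant infection. SAP section 15 declares no change in the planned analyses.

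**Vomiting within 1 hour.**

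- Protocol 7.1: "Subjects who vomit within 1 hour of study drug administration will be retreated for" the gonorrhea infection.
- Protocol 11.4.1: "To be compliant with study treatment, a subject must be able to swallow the pill and not vomit within 1 hour of administration". Compliance is a condition of PP, and SAP 3.3.6 and 6.3.2.3 agree.
- SAP 6.3.2.1 and 6.3.2.2 name vomiters as failures in ITT and micro-ITT. The PP paragraph does not mention them.

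**The concern.** PP is the population of the only confirmatory test, and the futility count in Protocol 11.3.1 and SAP 6.6 uses PP-eligible failures. A programmer cannot satisfy all of these sentences, and no order of precedence is given.

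The two readings push the result in opposite directions. If early re-treatment excludes a subject, PP loses subjects who are failures by the documents' own rule, and the cure rate is biased upward. If the failure sentence governs everything, vomiters who did not retain the dose count against the drug in an analysis meant for compliant subjects, and the cure rate is biased downward. The study is open-label, so an unresolved rule could be settled after outcomes are visible.

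**Working it through.** **Inputs.** All are from Protocol 11.1 and 11.2. The criterion is a "one-sided modified Jeffreys interval using a significance level of 0.05". The null hypothesis is that the proportion with "microbiological cure 5-10 days after receiving ciprofloxacin is less than 0.95". Power is computed "assuming a 98% microbiological cure rate", and "an evaluable target of 257 subjects is chosen". The shares of subjects dropped or vomiting are not in the documents and are assumed below.

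**The decision rule.** For X cures in N subjects (X < N), the lower bound is the 0.05 quantile of Beta(X + 0.5, N − X + 0.5). This is the lower limit from the code in SAP 6.1.1. (Protocol 11.4.3.1 prints the 0.95 quantile; that is a separate matter.)

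- 250/257 (7 failures): lower bound 95.19%, passes.
- 249/257 (8 failures): lower bound 94.70%, does not pass.

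**The plan's own figures.**

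- N = 257: power = P(Bin(257, 0.02) ≤ 7) = 85.4%; the plan says about 85%.
- N = 195 (limit 5 failures): power 80.2%; the plan says 80%.
- Enrollment: 257 / (0.75 × 0.90) = 380.7, so 381, as stated.

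**One subject.** Suppose the result is 250/257 with one re-treated subject left out. Counting that subject as a failure gives 250/258, with a lower bound of 94.72%. The conclusion reverses.

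**Exclusion reading.** Let q be the true failure rate and d the share of true failures that leave PP. The apparent failure rate is q(1 − d)/(1 − qd), and P(pass) = P(Bin(257, rate) ≤ 7). With q = 0.05:

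| d (assumed) | Apparent failure rate | P(pass) |
|---|---|---|
| 0% | 5.00% | 5.4% |
| 5% | 4.76% | 7.5% |
| 10% | 4.52% | 10.2% |
| 20% | 4.04% | 18.2% |
| 30% | 3.55% | 30.4% |

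**Failure reading for vomiters.** Let v be the share of subjects who vomit and count as PP failures, with 98% cure otherwise. The failure rate is 1 − 0.98(1 − v):

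| v (assumed) | Failure rate | Power |
|---|---|---|
| 0% | 2.00% | 85% |
| 0.25% | 2.25% | 78% |
| 0.5% | 2.49% | 69% |
| 1% | 2.98% | 50% |

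In 257 subjects, v = 1% is 2.57 people. By count, adding 1, 2 or 3 certain failures to the 257 leaves the limit at 7 in total and lowers power to 74.3%, 59.1% or 41.4%.

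**The case against.** A reader might infer that the SAP deletes known failures from the primary analysis. The documents do not support that, for two reasons.

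- *Known.* Outcome is defined by Visit 2 culture, and Protocol 7.4 schedules no culture at unscheduled or early-termination visits. A subject re-treated before Visit 2 is a failure by the documents' rule, not a culture-proven one, and could be a reinfection. Subjects found positive at Visit 2 are referred for treatment afterwards and stay in PP as failures. The affected group is narrow.
- *Deletes.* The SAP has not settled on deletion. Sections 6.3.2 and 6.3.2.1 and Table 4 carry the protocol's rule; one phrase in 6.3.2.3 conflicts with it.

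A reader might also infer that vomiters will be PP failures. The more natural reading of the SAP excludes them from PP and counts them as failures in micro-ITT and ITT. Only the general sentence, read literally over the specific compliance rule, says otherwise, so the power loss above applies only under that reading.

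Three further objections deserve an answer.

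- *Early discontinuation for lack of treatment effect is already a failure in every population* (Protocol 11.4.3.1, SAP 6.3.2.3 and 6.5). Investigator discretion and voluntary withdrawal leave room to document that reason, and no culture is needed. This is a real safeguard but a partial one. Lack of effect is not a listed withdrawal reason, whereas receipt of another systemic antibiotic is (Protocol 5.3.1), so the same subject may be recorded under the latter.
- *Dropping the word concomitant is not the only cause.* This is correct. Protocol 11.4.1 also excludes contraindicated medications. Section 6.2.7 points to 5.2 for these, and 5.2 lists antibiotics with potential activity against gonorrhea. The evaluability and visit-window conditions can remove the same subject. Restoring one word would not be enough.
- *The numbers affected may be very small.* They may, which is why the tables start at low shares. The margin is small too.

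**Conclusion.** The point stands as a contradiction in the population rules for the primary analysis, both between the documents and within the SAP. It does not show that the primary result will be biased in a known direction: the two readings pull opposite ways, and the documents give no frequency for early re-treatment or vomiting.

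What is certain is the sensitivity. With 7 failures allowed in 257, one reclassified subject can change the conclusion. The sizes rest on the assumed shares: P(pass) at 95% true cure moves from 5.4% to 7.5% with 5% of failures dropped and to 30.4% with 30% dropped; power at 98% cure moves from 85% to 78% with 0.25% vomiting and to 50% with 1%. The contradiction itself depends on none of these assumptions.

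**What to change.** Before database lock, state one analysis rule in both documents, with its precedence:

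1. A subject given non-study treatment for the study gonorrhea infection before Visit 2, after a compliant dose, is a failure in PP, micro-ITT and ITT. This overrides the PP exclusions for antibiotics or contraindicated medication, evaluability and visit window. The other PP conditions still apply.
2. A subject who is non-compliant through vomiting within 1 hour is excluded from PP and is a failure in micro-ITT and ITT.
3. A systemic antibiotic for another infection leads to exclusion from PP.

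In the text: restore the word concomitant in SAP 6.3.2.3; place rule 1 in SAP 6.3.2.2 and 6.3.2.3; limit the general failure sentence in Protocol 11.4.1 and SAP 6.3.2.1 so that it does not reach vomiters in PP; keep Table 4 aligned; and apply the same rule to the futility count.

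The cost is wording. The medication and compliance data are already collected (Protocol 6.2.6 and 6.2.7; SAP Listings 13 and 17). The downside is that a few more failures may count, including some possible reinfections. The change concerns classification only; no view is taken on whether or how any subject is re-treated.
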